### 1.7.1 Outcome 1 – MyChart adoption among participants without outpatient portal usage prior to enrollment was dependent on treatment

*Outcome specification:* A categorical variable identified whether the participants used the portal before the end of the cutoff period (1 = Admission New User or Post-Discharge New User; 0 = Never MyChart User). Prior MyChart Users were not included in the analysis for this outcome.

*Statistical model:* Logistic regression model with non-interacted and interacted study arms as binomial predictors.

*Covariates:* No covariates are added to this analysis.

### **1.7.2 Outcome 2 – MyChart adoption among participants without outpatient portal usage prior to discharge was dependent on treatment**

*Outcome specification:* A categorical variable identified whether the participants used the portal before the end of the cutoff period (1 = Post-Discharge New User; 0 = Never MyChart User). Prior MyChart Users and Admission New Users were not included in the analysis for this outcome.

*Statistical model:* Logistic regression model with non-interacted and interacted study arms as binomial predictors.

*Covariates:* No covariates were added to this analysis.

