3.1.1 Intervention description: Tech - Full/Lite

The Full-Tech intervention consisted of the standard build of the MyChart Bedside product as delivered from Epic and augmented by OSUWMC at the start of the study. The application was served by a *Home* landing page that displays events scheduled for the day and recent health updates and included access to 10 additional functions located in tabs along the side of the inpatient portal image:

1. *Home*: presented events scheduled for the day and data on patient vitals, including last blood pressure reading, current pulse and other patient vital signs refreshed from the Electronic Health Record (EHR) once every 5 minutesⁱ
2. *Bedside Tutorial*: tutorial materials for the use of MyChart Bedside, including an 11-minute video explaining how to use MyChart Bedside and access to PDF versions of tutorial materials
3. *Dining on Demand*: food ordering service
4. *To Learn*: educational resources for the patient based on their treatment plan
5. *Happening Soon*: a timeline for the care activities that the patient could expect for the day
6. *Taking Care of Me*: information detailing members of the patient's care team
7. *Messages*: non-urgent secure messaging with the patient's care team
8. *My Health*: recent vital signs and lab test results
9. *Notes*: write/record reminders and notes
10. *I Would Like*: non-urgent requests from pastoral care or gift shop
11. *OSU MyChart*: allowed the patient to access MyChart, including creating a new account

In addition to the *Home* landing page, the Lite-Tech version of MyChart Bedside consisted of the 3 functions: *Bedside Tutorial*, *Dining on Demand*, and *To Learn*.

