3.2.1 Tech randomization

Tech randomization was accomplished using a 4-digit random number table generated using Stata version 14.0 which was used as a comparison table against the last four digits of the patient's Medical Record Number (MRN) which was assigned prior to study assignment. A preliminary simulation analysis found that random assignment using this model created appropriately sized groups of 40% and 60%.

Individuals who had access to the Full version of MyChart Bedside prior to enrollment in the study (i.e., those patients who were admitted to the Cancer Center, which was not included as a site, or patients who had used MyChart Bedside during the pilot phase of implementation in which only Full-Tech was available) maintained their Full-Tech status and were excluded from randomization if they were transferred to a unit included in the study.

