3.2.2 Touch randomization

The study protocol included a series of robust approaches to randomization. Generally, Touch randomization occurred at consent using the randomizer function in Qualtrics which was used for both consent and survey data collection. The Protocol included a procedure for the assignment of Touch in cases where the patient was checked in after daily census and was not included in the Qualtrics randomization (i.e., due to timing of reconciliation between report pulls and the start of the work day). In those cases, a predefined randomization table was used to assign Touch status.

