## Section 1: Statistical analysis

### 1.1 Confidence intervals and p-values

For all statistical tests, a p-value of 0.05 was used to assess significance and 95% confidence intervals were reported. No adjustment was done for multiple hypothesis testing.

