### 1.4 Assumptions and testing

#### 1.4.1 Analysis populations

Estimates of the intervention effects were calculated on two analytic populations. The main analytic population of the study used an *intention-to-treat (ITT)* approach. Using this paradigm, participants were analyzed on the basis of the study group to which they were randomized, regardless of their eventual receipt of that intervention.

The effects of the intervention were additionally evaluated on a *per-protocol* population, composed exclusively by those participants who were administered their randomized intervention. The analysis of the data from the per-protocol population was weighted by the inverse of their probability to receive the intervention to which they were originally randomized, computed on the basis of the following demographic and clinical characteristics: sex, race, age at time of enrollment, Charlson Comorbidity Index, length of stay.

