### **1.7.3 Outcome 3 – MyChart adoption among participants who began using the outpatient portal during enrollment admission was dependent on treatment**

*Outcome specification:* A categorical variable identified whether the participants used the portal before the end of the cutoff period (1 = Admission New User; 0 = Never MyChart User). Prior MyChart Users and Post-Discharge New Users were not included in the analysis for this outcome.

*Statistical model:* Logistic regression model with non-interacted and interacted study arms as binomial predictors.

*Covariates:* No covariates were added to this analysis.

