### **1.7.4 Outcome 4 – Frequency of use for New MyChart Users.**

*Outcome specification:* The count of MyChart sessions occurring between the date of enrollment in the study and the cutoff date. This variable was specified as a count variable. Prior MyChart Users and Never MyChart Users were not included in the analysis for this outcome.

*Statistical model:* Negative binomial regression model for counts of sessions with non-interacted and interacted study arms as binomial predictors (see Equation 3).

Equation 3: If New MyChart User=1;  $y = X_{Tech} + X_{Touch} + X_{Tech*Touch}$

*Covariates:* No covariates were added to this analysis.

*Sub-sample analysis:* No sub-sample analyses were considered for this outcome.

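### H3 Outcomes 2, 3 and 4 select participants on MyChart adoption after assignment, so they are not randomised comparisons of adoption or use

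*SAP*

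**What the plan says.** SAP 1.4.1 makes intention-to-treat the main approach, in which "participants were analyzed on the basis of the study group to which they were randomized, regardless of their eventual receipt of that intervention". Tech follows the last four digits of the medical record number, which exists before study assignment (Protocol 3.2.1). In the usual process, "Touch randomization occurred at consent using the randomizer function in Qualtrics" (Protocol 3.2.2), and Protocol 3.3 places it before consent. Both assignments therefore precede anything a participant does with MyChart after enrolment.

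SAP 1.7 then sets five outcomes for H3:

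- Outcome 1 (1.7.1): any new adoption by the cutoff against never. Only Prior Users are left out.
- Outcome 2 (1.7.2): post-discharge adoption against never. "Prior MyChart Users and Admission New Users were not included in the analysis for this outcome".
- Outcome 3 (1.7.3): adoption during admission against never. "Prior MyChart Users and Post-Discharge New Users were not included in the analysis for this outcome".
- Outcome 4 (1.7.4): number of sessions. "Prior MyChart Users and Never MyChart Users were not included in the analysis for this outcome".
- Outcome 5 (1.7.5): number of sessions among Prior Users, which answers H3b.

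Outcomes 2 to 4 have no covariates, and no weighting or competing-event method is given for these exclusions. The weights in SAP 1.4.1 belong to the per-protocol population and model receipt of the intervention. The offset in SAP 1.4.2 adjusts for days with the tablet, not for who remains in the analysis. On testing, "a p-value of 0.05 was used to assess significance and 95% confidence intervals were reported", without adjustment for multiplicity (SAP 1.1).

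In Full-Tech, the OSU MyChart tab "allowed the patient to access MyChart, including creating a new account" (Protocol 3.1.1). It is not among the three selectable Lite-Tech functions.

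**The concern.** Adopting in hospital, adopting after discharge and never adopting are all results that follow assignment. Full-Tech acts directly on the first of them, because it offers account creation at the bedside. High-Touch may do so too within Full-Tech, because the navigator goes through each function (Protocol 3.1.2). The groups that Outcomes 2 and 3 remove can therefore be expected to differ by Tech arm. A change in when people adopt can then be read as a change in how many adopt.

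Outcome 3 is the clearest fault. Someone who adopted after discharge had not adopted during the admission, so that person belongs in the denominator as a zero. Outcome 3 instead removes the person because of a later event.

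Outcome 4 is a different problem. Moving adoption earlier or later within the follow-up window does not change who is in it. Its fault is that it conditions on having adopted. If the intervention draws in light users, mean sessions among adopters can fall while total use in the arm rises.

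At stake is what the trial may conclude on H3. With unadjusted tests at 0.05, such contrasts could be reported as benefit or harm from the intervention.

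**Working it through.** **The plan's own figure.** The documents give no design figure for H3. The only one is a planned enrolment of 3,872, with detectable changes of 2.2% to 3.8% in HCAHPS satisfaction scores (Protocol 3.4). It does not bear on this point.

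**Inputs.** From the documents: the category definitions (SAP 1.7.1 to 1.7.4), alpha 0.05 (SAP 1.1) and the counts in Protocol Table 2 (Full 2,147, Lite 745; High 901, Low 1,991). Assumed, because the documents give none: total adoption of 20% to 40%, split evenly by timing in the comparison arm; a shift of 2 to 10 points; and 30% to 70% of participants without prior use.

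**Step 1: pure timing shift.** Let a, p and n be the proportions adopting during admission, after discharge and never.

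- Outcome 1 OR = [(a₁+p₁)/n₁] / [(a₀+p₀)/n₀]
- Outcome 2 OR = (p₁/n₁) / (p₀/n₀)
- Outcome 3 OR = (a₁/n₁) / (a₀/n₀)

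Take 30% total adoption in both arms, with 20% and 10% (admission, after discharge) against 15% and 15%. Never is 70% in each.

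- Outcome 1: 30% v 30%, OR 1.00
- Outcome 2: 10/80 = 12.5% v 15/85 = 17.6%, OR = 10/15 = 0.67
- Outcome 3: 20/90 = 22.2% v 15/85 = 17.6%, OR = 20/15 = 1.33

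| Total adoption | Shift (points) | Outcome 1 OR | Outcome 2 OR | Outcome 3 OR |
|---|---|---|---|---|
| 30% | 2 | 1.00 | 13/15 = 0.87 | 17/15 = 1.13 |
| 30% | 5 | 1.00 | 10/15 = 0.67 | 20/15 = 1.33 |
| 30% | 10 | 1.00 | 5/15 = 0.33 | 25/15 = 1.67 |
| 20% | 5 | 1.00 | 5/10 = 0.50 | 15/10 = 1.50 |
| 40% | 5 | 1.00 | 15/20 = 0.75 | 25/20 = 1.25 |

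**Step 2: how often this would be called significant.** This used 20,000 multinomial replicates with pooled two-sided z-tests at 0.05. Participants were treated as independent, without the SAP's clustering or offset. Total adoption was 30%, the shift 5 points, and half of the Table 2 counts were without prior use.

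- Tech (1,074 v 372): Outcome 1 rejects 5%, Outcome 2 62%, Outcome 3 41%.
- Touch (450 v 996): 5%, 62% and 49%.
- Across 30% to 70% without prior use: Outcome 2 rejects 41% to 77%, Outcome 3 26% to 61%.
- With no shift, all three reject about 5%.

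Table 2 may reflect the reassignment of untreated High-Touch participants described in Protocol 4.3, so the Touch counts as randomised may differ.

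**Step 3: Outcome 4.** Assume that 20% adopt in the comparison arm at a mean of 10 sessions, and that the intervention adds 10% who adopt at a mean of 4.

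- Among adopters: (0.20×10 + 0.10×4)/0.30 = 8.0, ratio 8.0/10 = 0.80
- Per non-prior user: (2.0 + 0.4)/2.0 = 1.20

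If the added users average 2 sessions, adding 5% gives 0.84 among adopters and 1.05 per non-prior user. Adding 10% gives 0.73 and 1.10.

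**Step 4: would a multinomial model repair Outcomes 2 and 3?** Against Never, its odds ratios in the Step 1 example are (10/70)/(15/70) = 0.67 and (20/70)/(15/70) = 1.33, the same as before. Setting each category against everyone else moves them further from 1: (10/90)/(15/85) = 0.63 and (20/80)/(15/85) = 1.42. Absolute risks over all non-prior users show what happened: +5 points during admission, −5 after discharge, 0 in total.

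**The case against.** Five points can be made for the plan.

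- **Outcomes 2 and 3 may be meant as timing contrasts.** The title of Outcome 2 states its condition openly, and those who had not adopted by discharge are a recognisable at-risk set. This stands as a defence of description. It does not make the contrast a randomised one, because that set is formed after assignment. It does not help Outcome 3, which removes people for something they did later.
- **Outcome 4 resembles the second part of a hurdle analysis,** with Outcome 1 as the first. This also stands in part: counting never users as zero answers a different question. However, H3a concerns adoption and H3b concerns Prior Users, so adopters-only frequency tests neither. SAP 1.4.4 compared ordinary and zero-truncated negative binomial models, so the fit to many zeros would need checking.
- **The tests keep 5% size if the intervention changes neither timing nor adoption.** That is correct. A reader might infer that randomisation is lost for H3 as a whole. The documents do not support this: Outcomes 1 and 5 do not use these exclusions.
- **The sizes are assumed.** That is also correct. They show what can happen and do not estimate what did.
- **Restricting to people without prior use might seem harmless** because prior use precedes randomisation. For Tech the documents do not establish this. SAP 1.7 dates prior use to enrolment, while Tech follows the record number and the tablet must already have been accepted (Protocol 5.1.1). A Full-Tech patient could open MyChart through the tab before consenting and be classed as a Prior User. Outcome 1 shares this weakness.

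**Conclusion.** The point holds for Outcomes 2, 3 and 4. All three condition on behaviour after assignment that Full-Tech is built to affect, with nothing in the analysis to offset the selection. Outcomes 2 and 3 can depart from 1 in opposite directions when total adoption is unchanged. Over the assumed range, Outcome 2 runs from 0.87 down to 0.33 and Outcome 3 from 1.13 up to 1.67. Outcome 4 can reverse the direction of an effect on use, but through selection on adoption and not through timing.

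These figures rest on assumed adoption rates, timing splits and session means. H3 is secondary, so H1 and H2 are untouched. Outcome 1 drops no one for behaviour after enrolment and remains the sound test of H3a, subject to how prior use is dated. This should be corrected, because it changes what H3 can conclude.

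**What to change.** - Make Outcome 1 the only confirmatory test of H3a.
- Replace the inferential use of Outcomes 2 and 3 with absolute risks and risk differences by arm for adoption during admission, adoption after discharge and never. Put all non-prior users in the denominator, so that the two adoption risks sum to Outcome 1. Do not use multinomial-logit odds ratios against Never. The timing-specific risks will still differ if timing shifts, so read them beside the total.
- For Outcome 4, add a comparison of sessions per non-prior user with Never Users counted as zero, and check that the count model fits the zeros. Label the adopters-only result descriptive.
- Date prior use before tablet provisioning, or examine this in a sensitivity analysis. Do not state that it precedes randomisation for Tech.
- Define Admission New User and Post-Discharge New User. SAP 1.7 announces four groups, lists three and defines neither term.

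The cost is SAP wording and a small re-analysis of data already held, plus some model checking if the zeros fit poorly. The conditional contrasts lose their inferential status.

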### **1.7.3 Outcome 3 – MyChart adoption among participants who began using the outpatient portal during enrollment admission was dependent on treatment**

*Outcome specification:* A categorical variable identified whether the participants used the portal before the end of the cutoff period (1 = Admission New User; 0 = Never MyChart User). Prior MyChart Users and Post-Discharge New Users were not included in the analysis for this outcome.

*Statistical model:* Logistic regression model with non-interacted and interacted study arms as binomial predictors.

*Covariates:* No covariates were added to this analysis.

### **1.7.4 Outcome 4 – Frequency of use for New MyChart Users.**

*Outcome specification:* The count of MyChart sessions occurring between the date of enrollment in the study and the cutoff date. This variable was specified as a count variable. Prior MyChart Users and Never MyChart Users were not included in the analysis for this outcome.

*Statistical model:* Negative binomial regression model for counts of sessions with non-interacted and interacted study arms as binomial predictors (see Equation 3).

Equation 3: If New MyChart User=1;  $y = X_{Tech} + X_{Touch} + X_{Tech*Touch}$

*Covariates:* No covariates were added to this analysis.

*Sub-sample analysis:* No sub-sample analyses were considered for this outcome.

### 1.7.5 Outcome 5 – Frequency of use for Prior MyChart Users

*Outcome specification:* The count of MyChart sessions occurring between the date of enrollment in the study and the cutoff date. This variable was specified as a count variable. New MyChart Users and Never MyChart Users were not included in the analysis for this outcome.

*Statistical model:* Negative binomial regression model for counts of sessions with non-interacted and interacted study arms as binomial predictors (see Equation 4).

Equation 4: If Prior MyChart User =1;  $y = X_{Tech} + X_{Touch} + X_{Tech*Touch}$

*Covariates:* The count of pre-enrollment sessions was included as a covariate in the model to control for previous use.

*Sub-sample analysis:* No sub-sample analyses were considered for this outcome.

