Our proposed four-year study used a mixed-methods approach to evaluate a pragmatic randomized controlled trial (RCT) studying the effectiveness of a High-Tech Intervention (MyChart Bedside, the inpatient portal), and an accompanying High-Touch Intervention (training patients to use the portal to manage their care and conditions) in a sample of hospitalized patients. This study measured how a patient portal tailored to the inpatient stay could improve patient experience and increase patient engagement by 1) improving patients' perceptions of the process of care while in the hospital, 2) increasing patients' self-efficacy for managing their health and health care, and 3) facilitating continued use of a patient portal for care management activities after discharge. In addition, we aimed to enhance patients' use of the patient portal available to outpatients, MyChart, once they were discharged.

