5.1.1 Inclusion criteria

Study inclusion criteria were as follows:

1. patient accepted tablet and use of MyChart Bedside;
2. patient was available in their room; and,
3. patient was capable of informed consent.

Only patients who were provisioned with MyChart Bedside were included in the study.

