#### 1.4.8 Cutoff date determination

Two options were considered for both the pre-study enrollment and post-discharge cutoff dates as specified in subsequent sections: 90 days (approximately three months) and 180 days (approximately six months) before/after the hospital encounter in which an individual was enrolled in the study. The actual cutoff date was determined after examining the cumulative distribution of MyChart adoption over the course of the year preceding/following hospital discharge to identify a meaningful endpoint.ii

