#### 1.5.1 Outcome 1 – Number of MyChart Bedside sessions within the enrollment admission was dependent on treatment

*Dependent variable specification:* The count of MyChart Bedside sessions for the admission associated with study enrollment.

- Enrollment admission was defined as the admission when the patient was enrolled in the study.

*Statistical model:* Negative binomial model with non-interacted and interacted study arms as binomial predictors.

---

ii Preliminary analysis of adoption rates for the outpatient portal revealed a rapid decrease in the numbers following the first few months, which motivated us to set the value for the cutoff date at 90 days in order to more conservatively attribute portal use to an individual's participation in the study.

*Covariates:* No covariates were added to this analysis.

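### The H3b session count runs from in-hospital enrollment to day 90, so it mixes in-stay MyChart use, which only the Full-Tech portal has a built-in tab for, with use after discharge

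*SAP*

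**What the plan says.** - **Count window.** SAP 1.7.5 (Outcome 5, prior MyChart users) defines the outcome as "The count of MyChart sessions occurring between the date of enrollment in the study and the cutoff date". SAP 1.7.4 (Outcome 4, new users) uses the same window.
- **Start.** Enrollment takes place in hospital. Protocol 5.1.1 requires that the "patient was available in their room", and SAP 1.5.1 states: "Enrollment admission was defined as the admission when the patient was enrolled in the study".
- **End.** SAP 1.4.8 considers 90 or 180 days "before/after the hospital encounter in which an individual was enrolled in the study" and calls the later limit a post-discharge cutoff. Its footnote ii explains the decision to "set the value for the cutoff date at 90 days". (SAP 1.7 refers to 1.4.5 and 1.4.7 for sessions and cutoff; the definitions are in 1.4.6 and 1.4.8.)
- **Access by arm.** Protocol 3.1.1 lists an OSU MyChart function in the Full-Tech build that "allowed the patient to access MyChart, including creating a new account". Apart from the Home page, "the Lite-Tech version of MyChart Bedside consisted of the 3 functions" Bedside Tutorial, Dining on Demand and To Learn.
- **Training.** Under Protocol 3.1.2, High-Touch patients go through each function of their version with the navigator. In Full-Tech that includes the MyChart tab.
- **Aim.** Protocol 2.1 sets out to enhance patients' "use of the patient portal available to outpatients, MyChart, once they were discharged". H3b itself (Protocol 2.2, SAP 1.7) speaks only of higher use of MyChart.
- **Model.** Outcome 5 is a negative binomial regression on Tech, Touch and their interaction, with the pre-enrollment session count as covariate (SAP 1.7.5) and tablet-provisioning days as offset (SAP 1.4.2).

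**The concern.** The randomised Tech factor supplies a built-in route to the counted event, inside the counting window, in one arm. Suppose a Full-Tech prior user opens MyChart from the hospital tablet and afterwards uses it exactly as a comparable Lite-Tech patient does. If the Lite-Tech patient did not open MyChart in hospital by some other route, the Full-Tech count is higher although outpatient behaviour is the same. High-Touch training on the tab could produce the same pattern in the interaction term.

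What is at stake is interpretation. A positive H3b result could be read as evidence that the inpatient portal raised MyChart use after discharge, when part or all of it arose during the stay. Outcome 5 is the only H3b outcome, so no other planned analysis of prior users would show which it was.

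**Working it through.** The documents give no figure for H3b, so there is nothing to reproduce. The check is textual, followed by an illustration on assumed inputs.

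**1. What the window contains.** It starts at enrollment (in the room, during the admission) and ends 90 days after that hospital encounter. It is therefore the remaining stay plus 90 days. Protocol 6.3.8 drops stays under three days, so most participants probably have some in-stay time in the window. The interval from enrollment to discharge is not given.

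**2. Whether in-stay MyChart sessions are recorded.** SAP 1.7.1 to 1.7.3 distinguish Admission New Users from Post-Discharge New Users, so MyChart sessions during the stay are visible in the data. The documents do not state that a session opened through the tab is among them; that is an inference.

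**3. Whether the model removes them.** The covariate counts only sessions before enrollment. The offset scales by tablet days and subtracts nothing. It also covers tablet time only, while the count runs on to day 90. For adoption, SAP 1.7.2 excludes those who started during admission; the frequency outcomes have no such split.

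**4. Possible size (assumed inputs).** Let *m* be the mean Lite-Tech count over the window and *k* the net surplus of in-stay sessions per Full-Tech prior user, with post-discharge means equal and tablet days balanced between arms. Then

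rate ratio = (*m* + *k*) / *m*

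| | *k* = 0.25 | *k* = 0.5 | *k* = 1 | *k* = 2 |
|---|---|---|---|---|
| *m* = 3 | 1.08 | 1.17 | 1.33 | 1.67 |
| *m* = 5 | 1.05 | 1.10 | 1.20 | 1.40 |
| *m* = 10 | 1.025 | 1.05 | 1.10 | 1.20 |
| *m* = 20 | 1.01 | 1.025 | 1.05 | 1.10 |

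For example, *k* = 1 and *m* = 5 give 6/5 = 1.20. If Lite-Tech patients open MyChart in hospital as often by other routes, *k* = 0 and the ratio is 1.00.

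**5. Chance of a significant Tech term with no post-discharge difference.** Inputs: 2,147 Full-Tech and 745 Lite-Tech participants (Protocol Table 2); assumed 30% to 50% prior users and assumed negative binomial dispersion *a* of 1 to 2. A two-sided 5% Wald test on the log rate ratio uses

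SE² = (1/(*m* + *k*) + *a*)/n_Full + (1/*m* + *a*)/n_Lite

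Worked case: 50% prior users gives n = 1,073.5 and 372.5. With *a* = 1, *m* = 10 and *k* = 1, SE = √(1.0909/1,073.5 + 1.1/372.5) = 0.0630, and ln(1.1)/0.0630 = 1.51. The rejection probability is 32.8%.

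| | *k* = 0.5 | *k* = 1 |
|---|---|---|
| *m* = 5 | 13.2% to 30.5% | 35.5% to 79.3% |
| *m* = 10 | 7.2% to 12.1% | 13.5% to 32.8% |
| *m* = 20 | 5.6% to 6.9% | 7.2% to 12.4% |

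This ignores hospital clustering, the offset and the baseline covariate. It shows that a small surplus can matter when use is low; it does not describe the operating characteristics of the planned test.

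**The case against.** The strongest reply is that the outcome matches its hypothesis. H3b says higher use of MyChart and Outcome 5 is titled frequency of use; neither is limited to the period after discharge. Extra sessions through a Full-Tech tab are an effect of the randomised intervention, and starting the clock at study entry is a sound choice for the intention-to-treat analysis, since discharge comes later. Footnote ii also chose 90 days so that use could be attributed to study participation, and in-stay use is attributable to it. All of this stands: as a measure of all MyChart use since enrollment, the count is legitimate. What it does not do is show use after discharge, which Protocol 2.1 names as an aim and towards which the post-discharge cutoff points.

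Several stronger readings are tempting, and the documents do not support them:

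- **That the plan presents in-stay sessions as post-hospital use.** It never labels Outcome 5 that way.
- **That Lite-Tech patients had no route to MyChart in hospital.** They lacked the built-in tab. SAP 1.6.2b lists email, social media and researching health issues among tablet activities, and personal devices are not excluded.
- **That tab sessions certainly enter the count.** This is inferred, and SAP 1.4.6 discards zero-length sessions.
- **That the varying remaining stay biases the Tech contrast.** Nothing shows that stay differs by arm; variation alone adds noise.
- **That the post-discharge question goes unanswered altogether.** SAP 1.7.2 isolates post-discharge adoption among new users. Only frequency among prior users lacks a counterpart.

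**Conclusion.** The point holds as a limit on interpretation. Outcome 5 adds in-stay sessions to later ones, the built-in route to in-stay sessions exists in one Tech arm only, and nothing in the model separates the two. A positive Tech or Tech-by-Touch term for H3b may therefore partly reflect use of the hospital tablet. The likely direction favours Full-Tech, which is the hypothesised direction.

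The size cannot be determined. Session means, dispersion, the share of prior users and the net in-stay surplus are all absent from the documents, and the illustrated ratios, from 1.00 with no surplus to 1.67, rest wholly on assumptions. A reader might infer that any Tech effect on H3b would be false; that does not follow, because a true post-discharge effect may be present as well.

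H3 is secondary and the remedy is cheap, so this is something that should be fixed rather than an error that invalidates the plan.

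**What to change.** - **Outcome 5.** Make the H3b count the MyChart sessions from discharge of the enrollment admission to day 90 after it. Report in-hospital MyChart sessions separately by arm. Keep the enrollment-to-cutoff count as a sensitivity analysis, which preserves the comparison timed from study entry.
- **Outcome 4.** Keep the present window and report the count split at discharge. Starting at discharge would give zero counts to new users whose only MyChart use was during admission, although they are in that group because they used it.
- **Clarification.** State whether sessions opened through the OSU MyChart tab are written to the MyChart log. If they are not, the concern largely falls away.

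**Cost.** SAP wording and a re-cut of data already held. MyChart records are timestamped (SAP 1.4.6), encounter and outpatient-use tables share a participant identifier (Protocol 6.2), and admission and discharge times were already derived to link Bedside use to encounters (Protocol 6.3.4). The downside is a lower session count for the H3b analysis and one extra analysis to report.
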